#### **Mucositis or Hand/Foot Syndrome (HFS)**

If  $\geq$  grade 3 mucositis or HFS occurs, 5-FU/capecitabine will be interrupted for a minimum of 1 week. If the toxicity has not improved to  $<$  grade 2, the treatments will be held for up to 2 additional weeks. Once restarted, the dose of capecitabine will be reduced according to Table 2. If treatment is required to be held for  $\geq 3$  weeks, then study treatment will be discontinued.

#### **Other toxicities**

If  $\geq$  grade 3 toxicities directly attributable to 5-FU/capecitabine other than those discussed above occur (except fatigue, alopecia, or nausea/emesis in the absence of anti-emetics), therapy will be discontinued until the toxicity is  $<$  grade 2. If there is no evidence of tumor

progression, therapy may resume with a dose reduction according to Table 1. If treatment is required to be held for  $\geq$  3 weeks, then study treatment will be discontinued.

**TABLE 1: Capecitabine dose levels**

Dose Level	5-FU/Capecitabine Dose
-2	400 mg/m  per 21 day cycle
-1	600 mg/m 
0 ( starting dose)	800 mg/m 

## **5.2 Interferon Alpha-2b**

A dose reduction will be instituted upon any grade 3 or 4 toxicity that is attributable to Interferon alpha-2b. For all grade 3 or 4 toxicities related to IFN, the study treatment will be withheld for up to 3 weeks until the toxicity has resolved to CTCAE grade 1 or better, and then treatment may be restarted. Dose reduction/re-challenge for each toxicity criterion will be managed as discussed in the sections that follow. Patients will be withdrawn from the study if toxicity does not resolve to  $\leq$  CTCAE grade 1 within 3 weeks.

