### **3. PATIENT SELECTION**

#### **3.1 Inclusion Criteria**

- 3.1.1 Patients must have histologically or cytologically confirmed squamous cell carcinoma of the skin. Patients who present with "squamous cell carcinoma of unknown primary lesions" at the time of diagnosis will be eligible if patients have a plausible primary skin site removed in the past. Similarly, patients with neck, parotid, or facial lymph nodes positive for squamous cell carcinoma with no identifiable mucosal primary would also be eligible.

- 3.1.2 Patients must have measurable disease, defined by RECIST v1.1 as at least one lesion that can be accurately measured in at least one dimension of  $\geq 10$  mm by CT, MRI, or calipers. See section 9.2 for the evaluation of measurable disease.
- 3.1.3 There is no limitation to prior treatments with local, regional, topical or systemic agents, except for prior systemic treatment with 5-fluorouracil or prodrugs thereof. Prior topical treatment with 5-fluorouracil is permitted. Patients who are on chronic daily doses of prednisone of greater than 10 mg are excluded. There is no restriction on timing of last treatments as long as patients have recovered from all expected toxicities and at least 21 days have passed since last administration.
- 3.1.4 Age  $\geq 18$  years. Because no dosing or adverse event data are currently available on the use of 5-FU/Capecitabine or IFN alpha-2b in patients  $<18$  years of age, children are excluded from this study.
- 3.1.5 Life expectancy of greater than 3 months.
- 3.1.6 ECOG performance status  $\leq 2$  (Karnofsky  $\geq 60\%$ ; see Appendix A).
- 3.1.7 Patients must have normal organ and marrow function as defined below:
 

Absolute neutrophil count	$\geq 1,500/\text{mcL}$
Platelets	$\geq 75,000/\text{mcL}$
Total Bilirubin	$< \text{ULN}$ or up to 2x ULN if patient has clinically documented Gilbert's syndrome (elevated unconjugated bilirubin from decreased UGT1A1 activity)
AST(SGOT)/ALT(SGPT)	$\leq 2.5x$ institutional upper limit of normal or up to 5x ULN if known to be caused by liver metastasis
Creatinine Clearance	$\geq 50 \text{ mL/min}$ by either Cockcroft-Gault formula or 24 hr urine collection analysis.

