### **5. DOSING DELAYS/DOSE MODIFICATIONS**

#### **5.1 5-FU/Capecitabine**

A dose reduction will be instituted upon any grade 3 or 4 toxicity that is attributable to 5-FU/capecitabine. For all grade 3 or 4 toxicities related to 5-FU/capecitabine, the study treatment will be withheld for up to 3 weeks until the toxicity has resolved to CTCAE grade 1 or better (or back to baseline), and then treatment may be restarted. Dose reduction/re-challenge for each toxicity criterion will be managed as discussed in the sections that follow. Patients will be withdrawn from the study if toxicity does not resolve to  $\leq$  CTCAE grade 1 (or to baseline) within 3 weeks.

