#### **Myelosuppression**

On Day 1 of each cycle, if the neutrophil count is  $< 1000/\text{mm}^3$ , or the platelet count is  $< 75,000/\text{mm}^3$ , then treatment with 5-FU/capecitabine will be held until the neutrophil count is  $\geq 1000/\text{mm}^3$ , and platelet count is  $\geq 75,000/\text{mm}^3$ . Once restarted, 5-FU/Capecitabine will be dose reduced per Table 1. If treatment is required to be held for  $\geq 3$  weeks, then study treatment will be discontinued.

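### Section 5.1 contradicts its own subsections on whether return to baseline counts as recovery, and Section 5.2 omits baseline although Section 3.1.7 admits patients with abnormal liver tests

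*Combined protocol and SAP*

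**What the plan says.** **Section 5.1, general paragraph (5-FU/capecitabine).** After any attributable grade 3 or 4 toxicity, treatment is stopped for at most 3 weeks, and the restart condition reads "until the toxicity has resolved to CTCAE grade 1 or better (or back to baseline), and then treatment may be restarted". The withdrawal sentence carries the same alternative: a patient leaves only if the toxicity has not reached "CTCAE grade 1 (or to baseline) within 3 weeks". Between the two stands a deferral to the subsections: "Dose reduction/re-challenge for each toxicity criterion will be managed as discussed in the sections that follow".

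**Section 5.1, subsections.** Under Other toxicities, "therapy will be discontinued until the toxicity is" below grade 2, and study treatment is discontinued if the hold reaches 3 weeks. The diarrhea and mucositis/hand-foot rules also use below grade 2. None of the three mentions baseline. The myelosuppression rule works on counts instead: "treatment with 5-FU/capecitabine will be held until the neutrophil count is" at or above a stated value, with a matching platelet limit.

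**Section 5.2, general paragraph (interferon).** Treatment is withheld for up to 3 weeks "until the toxicity has resolved to CTCAE grade 1 or better, and then treatment may be restarted". The patient is withdrawn from the study if the toxicity has not come down to "CTCAE grade 1 within 3 weeks". Neither sentence mentions baseline.

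**Section 3.1.7 (eligibility).** AST/ALT may be up to 2.5 times the "institutional upper limit of normal or up to 5x ULN if known to be caused by liver metastasis". Bilirubin may be up to 2x ULN with documented Gilbert's syndrome.

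**The concern.** A rule that decides who stays on treatment should have one reading. Here the general paragraph of 5.1 and its subsection on other toxicities can give opposite answers for the same patient on the same day. Section 5.2, in almost the same words as 5.1, gives a third outcome.

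The difference has no effect on a patient who enters with normal values, because baseline is then already grade 1 or better. It matters for patients admitted with an abnormal value. Section 3.1.7 expressly admits such patients, and it does so on liver tests that the protocol expects the study drugs to affect. Section 6.2 lists elevated SGOT for interferon, and Section 6.1 lists hyperbilirubinemia for 5-FU/capecitabine. Such a patient could recover fully from the drug effect and still be stopped or withdrawn for the abnormality present at entry. Two investigators following the protocol could also handle identical cases differently.

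**Working it through.** The check is a comparison of texts. The plan gives no figure on this point to reproduce.

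**Step 1. Recovery criterion, rule by rule.**

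| Rule | Criterion | Baseline accepted? | If not met in time |
|---|---|---|---|
| 5.1 general | grade 1 or better | yes, in both sentences | withdrawn from study |
| 5.1 Myelosuppression | neutrophil and platelet counts | no | study treatment discontinued |
| 5.1 Diarrhea | below grade 2 | no | no restart, withdrawn from study |
| 5.1 Mucositis/hand-foot | below grade 2 | no | study treatment discontinued |
| 5.1 Other toxicities | below grade 2 | no | study treatment discontinued |
| 5.2 general | grade 1 or better | no, in either sentence | withdrawn from study |

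Baseline is accepted in 2 of 2 general sentences in 5.1, in 0 of 2 in 5.2, and in 0 of 4 specific 5-FU/capecitabine rules. Below grade 2 and grade 1 or better are the same threshold, so the only difference among the grade-based rules is the baseline alternative.

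**Step 2. Which rules govern liver tests.** For 5-FU/capecitabine, no named subsection covers them, so Other toxicities applies alongside the general paragraph. For interferon, the subsections cover fatigue, arthralgia/myalgia, weight loss, depression and gastrointestinal toxicity. None covers liver tests, so the 5.2 general paragraph stands alone. Weight loss (stabilization or start of recovery) and fatigue (no recovery grade stated) follow their own wording and do not bear on this case.

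**Step 3. Can the baseline be above grade 1?** Section 7 adopts CTCAE 4.0 but does not print its cut-offs. Let U be the upper limit of grade 1 as a multiple of ULN.
- AST/ALT with liver metastasis: entry values between U and 5 are above grade 1 if U is below 5. If U is 5 or more, none are.
- Bilirubin with Gilbert's syndrome: entry values between U and 2 are above grade 1 if U is below 2. If U is 2 or more, none are.

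**Step 4. Apply the rules.** Assume an entry value above grade 1, a rise in the same test to grade 3 or 4, return to the entry value within 3 weeks, and no further fall.
- Attributed to 5-FU/capecitabine, 5.1 general paragraph: restart allowed, no withdrawal.
- Attributed to 5-FU/capecitabine, 5.1 Other toxicities: no restart; study treatment is discontinued once the hold reaches 3 weeks.
- Attributed to interferon, 5.2: criterion not met; withdrawn from the study.

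The first two outcomes contradict each other for the same drug and event. The third is clear as written, but it takes no account of the entry limits in 3.1.7.

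**The case against.** **The subsections may simply control.** Section 5.1 defers to them for re-challenge, so on a specific-over-general reading both drugs share one threshold and attribution does not decide restart. This reading is fair, but it leaves the baseline wording in 5.1 without effect for any grade-based toxicity. The withdrawal sentence would still spare a patient whom the subsection stops.

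**The difference between 5.1 and 5.2 may be deliberate.** These are different drugs, and Section 2.2 names hepatic decompensation as a contraindication to interferon and hepatic failure as a severe reaction. This stands: the difference alone is not an error. The protocol does not say whether it is intended.

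**The diarrhea and mucositis/hand-foot rules matter little in practice.** Eligibility gives no allowance for these conditions at entry. Sections 3.1.3 and 3.2.1 require recovery from earlier treatment, and prior systemic 5-FU or its prodrugs is barred. This also stands; for those rules the conflict is one of wording.

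**Stronger readings that the documents do not support.**
- *Every such patient must be withdrawn.* Only 5.2 says so without contradiction. In 5.1 the text conflicts, and the mucositis/hand-foot and other-toxicity rules stop study treatment rather than withdraw the patient.
- *Uncertain attribution between overlapping toxicities decides who leaves.* Under their hepatic headings, 6.1 lists hyperbilirubinemia only and 6.2 lists elevated SGOT and right upper quadrant pain. Overlap on the same liver test is not shown.
- *Patients with liver metastases are lost selectively.* The protocol gives no frequency of liver metastasis.
- *The trial loses power.* With a fraction f of patients lost as responders, the response rate becomes 0.30 × (1 − f). Under the rules of at least 2 of 16 and at least 5 of 25, the exact chance of success is 0.903 at f = 0, 0.898 at 1%, 0.892 at 2% and 0.880 at 4%. Nothing in the documents sets f. One loss needs an entry value above grade 1, worsening of that test to grade 3 or 4, drug attribution, recovery to baseline but not to grade 1, and no response already secured. Patients who leave before completing one cycle are not evaluable under 11.2 and do not dilute the rate in this way.

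**Conclusion.** The point holds as an inconsistency of text. Section 5.1 gives two incompatible recovery criteria for grade 3 or 4 5-FU/capecitabine toxicity. The conflict has practical force under Other toxicities, where liver tests fall, and is one of wording only for diarrhea and mucositis/hand-foot syndrome. Section 5.2 has no baseline alternative and withdraws the patient from the study, and it is not aligned with the abnormal liver tests allowed at entry.

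The practical effect rests on one assumption: that some permitted entry values lie above CTCAE 4.0 grade 1, as set out in Step 3. The number of patients affected is unknown and probably small, because several conditions must coincide. No effect on the operating characteristics of the two-stage design is established.

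**What to change.** Reconcile the general paragraph of 5.1, its diarrhea, mucositis/hand-foot and other-toxicity rules, and the general paragraph of 5.2, with each other and with the entry limits in 3.1.7. State for each drug whether return to the patient's entry value counts as recovery, and apply that answer to both restart and withdrawal. If the two drugs are meant to differ, say so. Which criterion applies is for the investigators to decide.

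The cost is a few words in Sections 5.1 and 5.2. No new data are needed, since the study calendar in Section 8 already collects baseline bilirubin, AST and ALT.

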### **Fatigue**

If patient complains of severe fatigue ( $>gr3$ ), IFN will be held for the remained for the cycle. Upon starting the next cycle, patient will be placed in the dose "-1" group and managed according to table 2. If patient is unable to receive IFN for greater than 3 weeks, they will be withdrawn from the study.

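### Section 5.2's interferon fatigue rule and its general toxicity rule disagree on grade threshold, what is held, when to restart and when to withdraw

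*Combined protocol and SAP*

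**What the plan says.** Section 5.2 opens with a rule for interferon toxicity in general: "A dose reduction will be instituted upon any grade 3 or 4 toxicity that is attributable to Interferon alpha-2b". For the same grades, "the study treatment will be withheld for up to 3 weeks until the toxicity has resolved to CTCAE grade 1 or better". A patient whose toxicity has not come down to grade 1 within 3 weeks is withdrawn. Fatigue is not excepted. The paragraph then passes the detail on: "Dose reduction/re-challenge for each toxicity criterion will be managed as discussed in the sections that follow".

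The first of those sections is Fatigue. It begins "If patient complains of severe fatigue" and gives the threshold in brackets as greater than grade 3. The action is that "IFN will be held for the remained for the cycle", after which the patient starts the next cycle at dose level -1. Withdrawal follows if interferon cannot be given for more than 3 weeks. No recovery grade is stated.

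**The concern.** Two rules in one section govern the same expected toxicity and do not match. Fatigue is listed among the common adverse events of interferon in Section 2.2 and among the main influenza-like symptoms in Section 6.2, so the rule is likely to be used.

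Two patients with the same fatigue could be managed differently depending on which paragraph the treating physician follows. One could be held until recovery and withdrawn if recovery is slow; the other could be restarted at a reduced dose on a calendar date whatever the current grade. That bears on patient safety. It also bears on the safety profile, which is a secondary objective (Sections 1.2 and 11.1.2), because interferon exposure and the number of toxicity withdrawals would depend partly on which text was read.

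**Working it through.** This is a comparison of texts. The plan states no figure to reproduce.

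**Side by side, for fatigue attributed to interferon**

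| Element | General rule, Section 5.2 | Fatigue subsection, Section 5.2 |
|---|---|---|
| Grade 3 | Covered | Not covered as printed |
| Above grade 3 | Grade 4 covered | Covered |
| What is held | Study treatment | Interferon only |
| Length of hold | Until grade 1 or better, at most 3 weeks | Rest of the current cycle |
| Restart | On recovery, at a reduced dose | Next cycle, at level -1, no recovery grade |
| Withdrawal | Not at grade 1 within 3 weeks | Interferon not possible for more than 3 weeks |

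**Threshold.** For grade 3 the general rule applies and the fatigue rule does not. The general rule nevertheless sends the reader to the subsections for dose reduction and re-challenge, and the subsection for this toxicity has nothing on grade 3. The Depression and GI Toxicity subsections of 5.2 both name grades 3 and 4. Fatigue is the only interferon subsection with a numeric grade trigger that leaves grade 3 out.

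**If the sign is a slip.** Suppose the threshold was meant to include grade 3. The last four rows of the table are unchanged, so the two rules would still differ on what is held, for how long, when treatment restarts and when the patient is withdrawn. The Arthralgias and Depression subsections do state recovery to grade 1; Fatigue does not.

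**Size of the difference in dosing.** Interferon is given weekly (Section 4.3) in 21-day cycles, so there are 21 / 7 = 3 doses per cycle. If severe fatigue arises after the k-th dose of a cycle, holding for the rest of that cycle omits 3 - k doses:

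- k = 1: 3 - 1 = 2 doses omitted
- k = 2: 3 - 2 = 1 dose omitted
- k = 3: 3 - 3 = 0 doses omitted; the next dose is given on time at level -1

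The fatigue hold is thus fixed by the calendar. The general hold is fixed by recovery and can last up to 3 weeks wherever in the cycle the event falls. The gap is widest at k = 3.

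**Withdrawal.** Take a patient whose fatigue has fallen to grade 2 but no further at 3 weeks. The general rule withdraws this patient. Under the fatigue rule the next cycle has begun by then, so the patient may already be back on interferon at level -1, and the fatigue rule's own withdrawal condition is not met.

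**Other text on fatigue.** The only exception for fatigue in Section 5 is under Other toxicities in 5.1. It concerns toxicity attributed to 5-FU/capecitabine and does not reconcile the two interferon rules.

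**The case against.** The strongest reply is that grade 3 fatigue is already governed. The general rule covers every interferon-related toxicity of grade 3 or 4, and Table 2 supplies the reduced dose levels. A site following that rule alone would hold and reduce. A reader might infer from the fatigue threshold that grade 3 patients are to continue at full dose. The documents do not support this: the fatigue rule is silent on grade 3, and silence does not cancel the general rule. Where Section 5 wants to exempt fatigue, as in 5.1, it says so. This part of the reply stands.

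A second reply is that the sign is loose notation. The subsection speaks of severe fatigue, and the Depression subsection uses moderate for grades 1 and 2 with grades 3 and 4 as the next tier, which suggests that severe includes grade 3. A sign lost in reading the PDF cannot be excluded either, although the greater-than-or-equal sign survives in several subsections of 5.1. A slip is plausible, but it would settle only the threshold.

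A third reply is that the rules can be read together, since the rest of a 21-day cycle fits within a hold of up to 3 weeks and the general recovery condition could be carried over. That is a reasonable reading, but not a secure one: the general rule hands re-challenge to the subsections, and this subsection restarts at the next cycle without a recovery grade. It also leaves open whether 5-FU/capecitabine is held, because the general rule speaks of study treatment without defining it for this purpose.

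A reader might also infer an effect on the primary analysis through patients becoming non-evaluable. Section 11.2 asks for only one cycle of treatment for response evaluability, so at most an event that interrupts cycle 1 could matter, and Section 10.3 makes all patients evaluable for toxicity from first treatment.

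**Conclusion.** The inconsistency is real and no other text resolves it. As printed, the fatigue rule gives no instruction for grade 3. Where it does apply, it departs from the general rule on what is held, how long, when treatment restarts and when the patient is withdrawn. Those differences do not depend on how the sign is read.

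Per event, the fatigue rule omits 0 to 2 interferon doses when the fatigue follows a dose in that cycle, against a hold of up to 3 weeks and then withdrawal under the general rule. The dose count assumes weekly dosing without earlier delays. How many patients would be affected cannot be stated, because the documents give no expected frequency for fatigue of grade 3 or higher.

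The consequences are for patient safety, interferon exposure and the count of toxicity withdrawals. The Simon design figures in Section 11.2 (at least 2 responses in 16, then at least 5 in 25) are untouched. This should be corrected, but it does not undermine the design.

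**What to change.** The sponsor should reconcile the opening paragraph of Section 5.2 with its Fatigue subsection so that, for fatigue, the protocol gives:

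- one grade threshold;
- one statement of what is held (interferon alone or all study treatment);
- one restart condition, saying whether a recovery grade is required;
- one withdrawal condition.

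It would also help to state which text prevails when the general rule and a toxicity subsection differ. Which threshold and which conditions are clinically right is for the sponsor to decide.

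The cost is a short protocol amendment of a few lines, with IRB approval before implementation as Section 10.2.1 requires. Sample size, decision rules and data collection do not change.

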### **Arthralgias/Myaglias**

Pain management will initially be done with acetaminophen or ibuprofen as tolerated, or opiates as indicated. For severe toxicity, IFN will be held for 3 weeks and dose reduced according to Table 2. If not resolved to CTCAE grade 1 or better, patient will be removed from the study.

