**TABLE 2: IFN alpha-2b dose levels**

Dose Level	IFN alpha-2b
-2	1 mcg/kg SQ q week per 21 day cycle
-1	2 mcg/kg SQ q week per 21 day cycle
0 ( starting dose)	3 mcg/kg SQ q week per 21 day cycle

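### The interferon fatigue rule names one fixed restart level (−1) whatever reductions came before; read literally, it conflicts with the dose reduction that Section 5.2 requires for patients already at −1 or −2.

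*Combined protocol and SAP*

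**What the plan says.** Section 5.2 opens with a general rule for interferon: "A dose reduction will be instituted upon any grade 3 or 4 toxicity that is attributable to Interferon alpha-2b". It then passes the detail on: "Dose reduction/re-challenge for each toxicity criterion will be managed as discussed in the sections that follow".

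The Fatigue paragraph comes next. Its trigger and hold are: "If patient complains of severe fatigue ( $>gr3$ ), IFN will be held for the remained for the cycle". At the start of the next cycle the "patient will be placed in the dose '-1' group and managed according to table 2". The paragraph does not mention the level the patient was on when the fatigue occurred.

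The other interferon rules are worded differently. The arthralgia and myalgia rule reads: "For severe toxicity, IFN will be held for 3 weeks and dose reduced according to Table 2". The weight-loss, depression and GI rules likewise refer to reduction, or restart at a reduced dose, by Table 2. None of the four names a level.

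Table 2 has three levels and nothing below the third:

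- level 0 (start): "3 mcg/kg SQ q week per 21 day cycle"
- level −1: "2 mcg/kg SQ q week per 21 day cycle"
- level −2: "1 mcg/kg SQ q week per 21 day cycle"

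**The concern.** A restart level fixed in advance is a reduction only for a patient who is above it. A patient who has already been reduced, for fatigue or under one of the four other interferon rules, may be at or below −1 when severe fatigue occurs. For that patient the fatigue rule and the general rule point in different directions, and the general rule refers the reader back to the fatigue rule for its detail.

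The situation is not contrived. Section 4.3 plans weekly interferon for 27 weeks, and Sections 2.2 and 6.2 list fatigue among the common or expected toxicities. A second fatigue episode is enough to raise the question.

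What is at stake is a dosing instruction that applies after severe toxicity. Two clinicians could read it differently and each point to the text. Section 3.5 treats departures from the protocol made without agreement as non-compliance, so the safe handling of a patient should not depend on someone setting the wording aside. Safety is a secondary objective (Sections 1.2 and 11.1.2), and inconsistent handling would also blur the dose at which later adverse events arose.

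**Working it through.** No sample-size or error-rate figure is involved, and the plan states no figure to reproduce. The check is a comparison of the rules and a ratio of Table 2 doses.

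**Inputs.** Table 2: level 0 = 3, level −1 = 2, level −2 = 1 mcg/kg weekly. Fatigue paragraph: restart at level −1. General rule of Section 5.2: the dose must be reduced.

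**Step 1: literal effect of the fatigue rule.** Ratio = dose at level −1 ÷ dose at the current level.

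- From level 0: 2/3 = 0.67, a 33% reduction. Consistent with the general rule.
- From level −1: 2/2 = 1.00, no change. Not a reduction, so it conflicts with the general rule.
- From level −2: 2/1 = 2.00, a 100% increase. Conflicts with the general rule.

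**Step 2: how a patient gets there.** Assume that each reduction moves one level, which Table 2 does not itself say. Level −1 is reached after one fatigue episode, so a second episode gives the no-change case with no other toxicity involved. Under the literal reading, fatigue alone never takes a patient below −1. Level −2 therefore needs two earlier reductions, with the step from −1 to −2 made under another interferon rule. The increase is the rarer route.

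**Step 3: does other text settle it?** The general rule requires a reduction but hands the detail to the toxicity paragraphs; for fatigue, that is the sentence in question. The reference to Table 2 could mean stepping down from level to level, but the table only lists doses and contains no stepping instruction. If the general rule is taken to govern, a patient at −1 has only one lower entry in Table 2, level −2 (1/2 = 0.50). A patient at −2 has none.

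**Step 4: the bottom of the table.** At −2 the required reduction has no Table 2 entry. This holds for every interferon toxicity and does not depend on how the Fatigue paragraph is read. Section 5.2 withdraws patients whose toxicity does not settle to grade 1 within 3 weeks. For toxicity that does settle, only the general provisions remain: removal for unacceptable toxicity (Section 3.5) and ending treatment for unacceptable adverse events (Section 4.4).

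**Step 5: the trigger.** The general rule covers grades 3 and 4. The fatigue trigger is written as above grade 3, which literally leaves out grade 3. Grade 3 fatigue then falls under the general rule, whose detail is left to a paragraph that does not cover it.

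**The case against.** A reader might infer that the protocol sends every patient to −1 whatever the current level, so that a site following the text would double the dose of a patient at −2. The documents do not support that.

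- The Fatigue paragraph is silent on the current level; it does not say that it applies at all levels. It reads naturally as describing a patient at the starting dose, with the reference to Table 2 covering later steps.
- The general rule belongs to the same section and calls for a reduction. Section 4.3 also speaks only of dose reductions under Section 5, and nothing in Section 5 provides expressly for an increase. A site that raised the dose would breach the general rule.
- The absence of a level below −2 is not a defect of the fatigue rule. It affects all the interferon rules, and Table 1 for 5-FU/capecitabine also stops at −2. Sections 3.5 and 4.4 allow removal or stopping, so the patient is not left without any provision.
- The problem depends on an earlier reduction. The documents give no frequency, enrolment is 30 patients, and dose intensity is not a listed endpoint.

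These points stand, and they limit the finding. They do not remove it. The general rule gives the detail away to the Fatigue paragraph, that paragraph alone names a level, and the table supplies no stepping rule. For a patient already at −1, literal placement at −1 and the required reduction cannot both be followed. That is a conflict between two stated instructions, not only a missing detail.

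**Conclusion.** The fatigue rule is wrong as written, within limits. Read literally, it gives no reduction from −1 (2 to 2 mcg/kg) and an increase from −2 (1 to 2 mcg/kg), and both conflict with the general rule. The no-change case is the more plausible, because a repeat fatigue episode is enough to produce it. The doubling is a consequence of the words taken alone. It should not be reported as what the protocol intends or as what sites would do.

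Two smaller defects stand on their own: no reduction is available at −2 for any interferon toxicity, and the fatigue trigger does not match the grades in the general rule.

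The conclusion assumes that Table 2 is the complete list of interferon levels and that a patient may stay on study after an earlier reduction, as Section 5.2 allows. How many patients would be affected cannot be derived from the documents. The response analysis does not depend on the point. It is a safety-related clarification that is worth making, but not a flaw that undermines the design.

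**What to change.** Reconcile three places in Section 5.2: the general rule, the Fatigue paragraph and Table 2. The revised text should:

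- state what applies after severe fatigue in a patient already at −1 or −2, in a way that agrees with the general rule;
- make the instruction at −2 one that can be carried out, for all interferon toxicities;
- use the same trigger grade in the Fatigue paragraph and in the general rule.

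The clinical team must decide the content; this review does not say which reading or dose is right. The cost is one or two sentences in a protocol amendment, with no change to sample size, endpoints or analysis.
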